In 2022 a meta-analysis performed by (**Grawish et al., 2022**)⁽²³⁾ indicated that DDM as a regenerative biomaterial has potential roles in tissue regeneration. However, in order to confirm these trials, further well-designed analyses are needed, and evaluation of adverse events in observational studies is also needed.

To our knowledge, DDM has not been investigated as scaffold in regenerative endodontics for permanent teeth.

Several studies were evaluate the regenerative effect of DDM at dentin-pulp complex through direct pulp capping technique, and it was found to possess the ability to activate the odontogenic differentiation of stem cells resident in the pulp tissues and induce reparative dentin formation. DDM also considered for alveolar ridge, maxillary sinus floor augmentations, socket preservation, furcation perforation repair, guided bone, and bioroot regenerations as well as bone and cartilage healing ⁽²³⁻²⁷⁾.

Hence, this study will be designed to evaluate regenerative effect of Demineralized Dentin Matrix as a scaffold in comparison to conventional blood clot in immature permanent teeth.

II. The null hypothesis

The null hypothesis is that there are no significance differences in the clinical and radiographic outcomes of regenerative endodontic of non-vital immature permanent teeth following the use of DDM in comparison to a blood clot scaffold.

III. Aim of the study

This study aims to:

Compare the clinical and radiographic outcomes of demineralized dentin matrix scaffold to blood clot scaffold in immature permanent incisors with non-vital pulps for one year.

IV. PICOTS

P: Patients ranging age 7–13years

I: Demineralized Dentin Matrix as a scaffold in Regenerative endodontic procedure

C: Blood clot scaffold Regenerative endodontic procedure

O: Clinical and radiographic success.

T: One year

S: outpatient's clinic of the Pediatric Dentistry and Dental Public Health Department, Faculty of Dentistry, Ain Shams University.

V. Methodology:

i. Study design

A Randomized, Controlled trial with 1:1 allocation ratio

ii. Sample size estimation

A power analysis was designed to have adequate power to apply a two-sided statistical test of the null hypothesis that there is no difference would be found between different groups. By adopting an alpha level of (0.05) a beta of (0.2) i.e. power=80% and an effect size (d) of

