(1.51) calculated based on the results of a previous study ⁽²⁵⁾. the predicted sample size (n) was a total of (24) cases (i.e. 12 cases per group). Sample size was increased by 20% to compensate for possible dropouts during follow-up intervals to be (30) cases (i.e. 10 cases per group). Sample size calculation was performed using G*Power version 3.1.9.7⁽²⁸⁾

iii. Assignment of intervention:

a. Randomization and Allocation concealment.

1- Type: block Randomization, with blocks numbers of 10 and 1:1:1 allocation ratio in to 3 groups

Group I: DDM (study)

Group II: (control) blood clot

Group III: (+ control) blood clot with collagen

2- Sequence generation: the most senior supervisor will generate the sequence of random numbers using online randomization (www.random.org).

Allocation concealment and implementation:

Allocation concealment will be ensured by preparing opaque envelopes containing one number from the generated random sequence for assigned group. The most senior supervisor will select an envelope and reveal the treatment group at the final regeneration visit.

b. Blinding:

double blind study, participants, outcome assessors, statistician will be blinded.

iv. Study setting

This study will be conducted at the Outpatients Clinic at the Department of Pediatric Dentistry and Dental Public Health, Faculty of Dentistry, Ain Shams University.

ii. Study methodology

ethical regulation:

The study protocol will be submitted to the Research ethics committee, Faculty of Dentistry, Ain Shams University for approval.

V. Population

All parent or legal guardian fulfill the eligible criteria will be signed an informed consent before beginning any procedure, explaining detailed treatment procedures, the possible outcomes, comprehensive discussions of the risks, complications, alternative treatment options, follow-up period needed, and sequel of no treatment⁽⁸⁻¹⁴⁾.

Inclusion criteria:

- (1) Age 7–13 years at the time of enrolment.
- (2) Provision of informed consent by one parent or legal guardian.
- (3) At least one immature permanent anterior tooth diagnosed with irreversible pulpitis or pulp necrosis with or without periapical lesions.
- (4) Restorable teeth.
- (5) Compliant patient/parent.
- (6) Patients not allergic to medicaments and antibiotics necessary to complete procedure (ASA 1 or 2).
- (7) Radiologic evidence of open apices (Teeth are considered immature when a minimum of 1 mm apical foramen width is evident)

Exclusion criteria

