- (1) Teeth with root fractures or split roots.
- (2) Presence of root resorptions.
- (3) Presence of periodontal pockets.
- (4) Developmental anomalies
- (5) Presence of periapical radiolucency more than 10 mm
- (6) Tooth with class III mobility.

vi. Clinical Procedures

a. Screening Recruitment

Patients attending the outpatient's clinic of the Pediatric Dentistry and Dental Public Health Department, Ain Shams University will be screened for eligibility. Only patients who met the inclusion criteria and sign the informed consent will be conveniently enrolled in the study until

the predetermined sample size is reached. All examination procedures will be done by the same operator to ensure standardization.

b. Informed Consent

A signed informed consent from parent or legal guardian, and an oral assent to the child, as outlined by the Research Ethics Committee, Faculty of Dentistry, Ain Shams University will be obtained before the conduction of the study.

Grouping:

Eligible immature anterior teeth will be randomly allocated in two groups:

Group I: 10 teeth will be treated with demineralized dentin matrix as scaffold in regenerative endodontic procedure.

Group II: 10 teeth will be treated with conventional regenerative endodontic procedure (blood clot scaffold).

Group III: 10 teeth will be treated with regenerative endodontic procedure (bloodclot and collagen scaffold).

Clinical procedures:

Pre-operative periapical radiograph and cone beam computed tomography CBCT will be taken on the selected non-vital tooth in each child before the beginning of the regenerative endodontic treatment procedure (29, 30).

RET will be carried out according to ASE⁽⁸⁾

First Appointment

- Local analgesia will be delivered (2% lidocaine with 1:100,000 adrenaline).
- Following rubber dam isolation and access cavity preparation, pulp tissue extirpation/debridement
- The root canal system will be minimally instrumented.
- Copious irrigation will be performed, gently with 20ml NaOCl (1.5% NaOCl (20mL/canal, 5 min) using 0.3mm gauge single side vented needles, adjusted 3 mm short of the apex.
- then canal will be irrigated with EDTA (20 mL/canal, 5 min), with irrigating needle that will be positioned about 1 mm shorter than the root end, to minimize cytotoxicity to stem cells in the apical tissues, followed by a final rinse 20 mL sterile saline .

- Canals will be dried with paper points.

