In group III: teeth will be treated with conventional regenerative endodontic procedure (blood clot and collagen scaffold).

Teeth, in this group, will be anaesthetised using a local anaesthetic without vasoconstrictor. Bleeding will be created into root canal by over-instrumentation

A collagen will be placed into the canal, apical to the CEJ.

Placement of the bioactive and restorative materials as mentioned above

e. Follow up

Clinical and Radiographic examination will be carried out during follow up period^(15, 16).

1- Clinical evaluation: Treatment success will be assessed using following criteria of success.

Criteria of success: Absence of

- Pain
- Soft tissue swelling
- Soft tissue inflammation
- Sinus tract
- tenderness to percussion
- tooth mobility

2- Radiographic evaluation:

A-Conventional radiographic evaluation:

Criteria of success:

- Apical foramen width reduction
- Increased dentinal wall thickness
- Increased root length
- Conventional radiograph showing progress bone healing and presence of a normal periodontal ligament space.
- Reduction in size of the lesion.

B- CBCT evaluation:

- CBC with limited field of view will be carried out at 12 month to asses dentin width and length^(23, 28)

f. Outcome measurement

Outcome	assessment	Assessment method
Primary outcome	1- pain 2-pain percussion 3-pathological mobility 4- gingival becket	1-visual assessment 2-percussion test 3-blunt ends of two examination mirrors 4-graduated metal periodontal probe
Secondary out com	1-Root length 2-Root dentinal thickness 3- Apical foramen width 4- Total radiographic root area (absence of internal and external root resorption, widening of periodontal ligament space, new preabical radiolucencies or enlargement of pre-existing lesion, pulp canal calcification)	Digital periapical radiograph examination with using paralleling device
Secondary outcome	Increased root wall thickness and increased root length.	CBCT with limited field of view

VII. Statistical analysis

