Categorical data will be represented as frequency (n) and percentage (%) and will be analyzed using chi square test. Numerical data will be explored for normality by checking the data distribution, calculating the mean and median values and using Kolmogorov-Smirnov and Shapiro-Wilk tests. If the data was found to be normally distributed, it will be presented as mean and standard deviation values and paired t-test will be used for the analysis. If the assumption of normality was found to be violated; the data will be presented as median and range values and will be analyzed using Signed rank test. The significance level will be set at $p \leq 0.05$ for all tests. Statistical analysis will be performed with IBM SPSS Statistics Version 26 for Windows.

VIII. Study timeline

This study will be conducted from October 2023 to October 2024.

X. Patient withdrawal

- Patients who aren't willing to continue in the study will have the right to quit at any time without loss of any benefits.
- Patients who don't comply with the oral hygiene measures given will be excluded from the study and will be offered to continue dental treatment at the departments' outpatient clinic.
- Any adverse event will be recorded and managed promptly. In addition, in failure occurs, the use of the experimental material will be stopped and patients will be treated with another modality.

[figure not shown]
xi. Data management

Patient information will be guarded as confidential information that should never be revealed at all times.

All information will be kept as a hard and soft copy.

xii. Adverse event reporting

Regenerative treatment is not expected to have any adverse side effects on health but if failure occurs in the regenerative treatment, conventional regenerative endodontic treatment will be fabricated.

xiii. Ethics and dissemination

a. Research ethics approval:

This protocol and the template informed consent form contained in Appendix are written following the guidelines outlined by the Research Ethics Committee and Institutional Review Board, Faculty of Dentistry, Ain Shams University.

b. Protocol amendments:

In case of protocol modifications, the Research Ethics Committee and Institutional Review Board, Faculty of Dentistry, Ain Shams University will review and approve the changes of protocol before proceeding and implementation of changes.

c. Informed consent:

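### No planned comparison of arms uses the pre-operative root measurement, so precision on the secondary radiographic outcomes may be lost with 8 to 10 teeth per arm

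*Protocol*

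**What the plan says.** Baseline imaging is part of the plan. Under Clinical procedures, "Pre-operative periapical radiograph and cone beam computed tomography CBCT will be taken on the selected non-vital tooth in each child". Under e. Follow up, "CBC with limited field of view will be carried out at 12 month to asses dentin width and length". The table in f. Outcome measurement lists root length, root dentinal thickness and apical foramen width on periapical radiographs as secondary outcomes. It lists wall thickness and root length on CBCT as a further secondary outcome. The success criteria and the CBCT row word these as increases or reductions, so they need a starting value. The primary outcomes are clinical: pain, pain on percussion, mobility and a periodontal-probe item.

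Section VII assigns tests by data type: chi-square for categorical data, and for numerical data a "paired t-test will be used for the analysis" if normal or a signed rank test if not. It names no covariate and no model.

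Entry is open to ages 7 to 13 with an apical opening of at least 1 mm. Section iii (Assignment of intervention) describes blocks of 10, three groups and no stratification by root stage.

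**The concern.** A paired t-test or signed rank test uses the baseline only within an arm, to ask whether teeth changed. It does not compare DDM with blood clot. Section VII therefore gives the trial no arm comparison for its root measurements, and none that uses the pre-operative value.

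The obvious repair would be an unpaired test of 12-month values, which would still ignore the baseline. Teeth entering over a six-year age span will differ in root length, wall thickness and foramen width before treatment. With arms this small, one arm can start with more mature roots by chance. A 12-month comparison then mixes starting stage with scaffold effect, and the between-tooth spread widens the confidence interval. At stake is how precisely the trial can describe root development, which is the radiographic half of its stated aim.

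**Working it through.** **Teeth per arm.** Section ii (Sample size estimation) gives two-sided alpha 0.05, 80% power and d = 1.51. A two-sample t-test (noncentral t) then needs 7.97, so 8 per arm (power 80.2%). Three arms of 8 make 24, and 24/0.8 = 30, or 10 per arm. Both stated totals reproduce. The 12 in "the predicted sample size (n) was a total of (24) cases (i.e. 12 cases per group" does not fit three arms: 3 × 12 = 36, and 12 per arm would have 94.2% power. The plan then says "Sample size was increased by 20% to compensate for possible dropouts during follow-up intervals to be (30) cases (i.e. 10 cases per group". I therefore use 8 (evaluable) and 10 (recruited) per arm.

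**Chance imbalance at baseline.** The difference between two arm means has SD √(2/n) in units of the baseline SD.
- n = 8: √(2/8) = 0.50. P(|difference| > 0.5 SD) = 2[1 − Φ(0.5/0.50)] = 32%.
- n = 10: √(2/10) = 0.447. P(|difference| > 0.5 SD) = 2[1 − Φ(0.5/0.447)] = 26%.

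**What a gap of 0.5 SD does, given that it is seen** (equal variances at both times). A comparison of 12-month values shifts by 0.5r SD: 0.25, 0.35 and 0.45 at r = 0.5, 0.7 and 0.9. A comparison of changes shifts the other way by 0.5(1 − r) SD: 0.25, 0.15 and 0.05.

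**Variance of the arm difference.** The correlation r is an assumption, because the protocol gives none. Relative to comparing 12-month values (factor 1), the factors are:
- change score: 2(1 − r);
- ANCOVA: (1 − r²)(1 + 1/(2n − 5)), where the second term allows for estimating the slope in a small trial. At n = 8 it is 12/11 = 1.091.

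Variance ratios and power at n = 8 per arm, for a true difference of 1 SD:

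| r | ANCOVA / 12-month values | ANCOVA / change | Power: 12-month | change | ANCOVA |
|---|---|---|---|---|---|
| 0.5 | 0.75 × 1.091 = 82% | 0.818/1.0 = 82% | 46% | 46% | 54% |
| 0.7 | 0.51 × 1.091 = 56% | 0.556/0.6 = 93% | 46% | 67% | 70% |
| 0.8 | 0.36 × 1.091 = 39% | 0.393/0.4 = 98% | 46% | 84% | 84% |
| 0.9 | 0.19 × 1.091 = 21% | 0.207/0.2 = 104% | 46% | 99% | 98% |

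The correction 1 + 1/(2n − 4) = 13/12 would lower each ratio by about one point or less, for example to 81/92/97/103% against change. At r = 0.3, ANCOVA gains almost nothing over 12-month values (99% of the variance), but has 0.993/1.4 = 71% of the variance of a change score.

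At the planned d = 1.51 with 8 per arm, power for 12-month values, change and ANCOVA is 80/80/87% at r = 0.5 and 80/95/96% at r = 0.7. The protocol does not say which outcome d = 1.51 refers to.

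**Validity check.** In simulation (20,000 trials per setting; r = 0.5, 0.7 and 0.9; n = 8 and 10), the type I error of all three analyses stayed near 5%.

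**The case against.** The strongest reply is that covariates are commonly left to the statistical analysis plan, which is not shown, and that the quoted sentence has a more basic fault: a paired test does not compare independent arms. Both statements are true, and silence about adjustment alone would not be a finding. But section VII is not silent. It commits to named tests, none of which can carry a covariate. Replacing the paired test with an unpaired one would not bring the baseline in.

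A second reply is that the root outcomes are worded as change, so the likely comparator is a change score, against which the gain is modest. This stands. From r = 0.7 upward the variance saving is 7% or less, and at r = 0.9 ANCOVA is slightly worse. The large gains are against 12-month values. Since section VII does not say which quantity would be compared between arms, both comparators must be shown.

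Third, the protocol says that images are taken before treatment, not that root dimensions are measured on them. That is an inference, though a strong one, because an increase cannot be scored without a starting value.

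A reader might also infer that an unadjusted comparison would be biased or would raise the false-positive rate. Neither follows. Under randomisation the estimate is unbiased on average, and the type I error holds near 5%. The shifts shown above apply only given an observed imbalance.

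**Conclusion.** The point holds as a matter of precision on secondary outcomes. Section VII fixes a numerical analysis that leaves the pre-operative value out of any arm comparison. With 8 to 10 teeth per arm, a baseline gap above 0.5 SD between two arms is expected in 26% to 32% of trials. Adjustment removes 18% to 79% of the variance of a 12-month comparison as r goes from 0.5 to 0.9. Against a change score it removes 18% at r = 0.5, 7% at 0.7 and 2% at 0.8, and adds 4% at 0.9.

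These figures rest on the assumed r, equal variances at the two times, a linear relation, and root dimensions being read from the pre-operative images. The imbalance chances also treat baseline means as normal.

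Two stronger readings are not supported. The primary outcomes are clinical signs and are untouched by this point. Nor does adjustment always shorten the interval: it can lose slightly to a change score when r is about 0.9. It is worth doing because it supplies the missing arm comparison, is never materially worse than either alternative over r = 0.3 to 0.9, and needs no prior knowledge of r.

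**What to change.** In section VII, state that each numerical root measurement at 12 months (root length, dentinal thickness, and apical foramen width on the periapical radiograph) is compared between arms by a linear model. Its terms are arm and the same tooth's pre-operative value by the same imaging method. Include all randomised arms, name DDM minus blood clot as the main contrast, and report adjusted differences with 95% confidence intervals. If residuals are clearly non-normal, use a rank-based version of the same model in place of the signed rank test. Keep within-arm paired tests as description only. State also that root dimensions are measured on the pre-operative images.

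The cost is a few sentences and one degree of freedom per model. It needs no extra patients or imaging. If r is about 0.9, the loss against change scores is trivial: about 4% of the variance at 8 per arm.

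### Normality checks on 8 to 10 teeth per arm choose the test for numerical outcomes but add no protection; fix one between-arm analysis in advance (minor)

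*Protocol*

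**What the plan says.** Section VII (Statistical analysis) sets a rule with three parts.

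- The check: "Numerical data will be explored for normality by checking the data distribution, calculating the mean and median values and using Kolmogorov-Smirnov and Shapiro-Wilk tests".
- When the checks are passed: "it will be presented as mean and standard deviation values and paired t-test will be used for the analysis".
- When they fail, the signed rank test applies and the summary changes too: "If the assumption of normality was found to be violated; the data will be presented as median and range values".

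One significance level, 0.05, is set "for all tests. Statistical analysis will be performed with IBM SPSS Statistics Version 26 for Windows". No separate threshold is given for the normality tests.

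The outcome table (section f, Outcome measurement) places root length, dentinal thickness, apical foramen width and root area among the secondary outcomes. The primary outcomes are four clinical signs, of which only the periodontal probe reading could be numerical. The Grouping section assigns 10 teeth to each of three arms, and the sample size section allows for 20% dropout.

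**The concern.** The outcome data choose between a mean-based and a rank-based test, and between two kinds of summary. The two tests address different quantities. A screening step of this kind is worth having only if it detects the departures that would damage the t-test. With 8 to 10 observations per arm that is doubtful.

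Two things are at stake. The first is whether the switch improves error control. The second is whether the reader will see one consistent comparison of scaffolds for each outcome, which is what the null hypothesis and the aim of the study call for.

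**Working it through.** **1. Inputs.** Alpha 0.05 and power 80% ("By adopting an alpha level of (0.05) a beta of (0.2) i.e. power=80"), a two-sided test ("adequate power to apply a two-sided statistical test of the null hypothesis"), d = 1.51, 20% dropout and three arms of 10, all from the sample size, assignment and grouping sections. The protocol gives no standard deviation or shape for any outcome, so the shapes below are assumptions. The normality tests are assumed to run at 0.05.

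**2. The plan's own figure.** A two-sample t-test (noncentral t) with d = 1.51 needs 7.97, so 8 per arm (power 0.802). Then 8 × 3 = 24, 24 / (1 − 0.20) = 30, and 30 / 3 = 10 per arm. The totals of 24 and 30 reproduce for three arms. The label of 12 per group fits 24 / 2, not three arms; that is a separate inconsistency. The working range here is therefore 8 to 10 teeth per arm.

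**3. Power of the checks** (20,000 simulated samples per row; Kolmogorov-Smirnov with Lilliefors critical values). Entries are the percentage of samples flagged as non-normal.

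| Assumed shape | Skewness | Shapiro-Wilk, n = 8 / 10 | K-S, n = 8 / 10 |
|---|---|---|---|
| Normal | 0 | 5.2 / 5.1 | 5.0 / 4.9 |
| Gamma, shape 4 | 1.0 | 11.0 / 14.0 | 9.2 / 10.4 |
| Gamma | 1.5 | 19.8 / 26.8 | 14.7 / 18.3 |
| Lognormal, sigma 0.5 | 1.75 | 18.8 / 24.5 | 14.5 / 17.4 |
| Exponential | 2 | 33.3 / 44.0 | 23.4 / 29.1 |

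At skewness 1.0 to 1.5, Shapiro-Wilk misses 100 − 26.8 = 73% to 100 − 11.0 = 89% of samples.

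**4. Effect on type I error** (10,000 samples per row). The within-arm columns test a true mean change of zero. Two-stage means the signed rank test if Shapiro-Wilk rejects, otherwise the t-test. The last column is an independent two-arm comparison: Welch t-test if both arms pass, otherwise Mann-Whitney.

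| Shape, n | Always t | Two-stage | t among samples that pass | Two-arm two-stage |
|---|---|---|---|---|
| Normal, 8 | 5.3% | 5.3% | 5.3% | 5.0% |
| Normal, 10 | 5.2% | 5.1% | 5.1% | 5.1% |
| Skewness 1.0, 8 | 6.5% | 6.5% | 6.9% | 4.9% |
| Skewness 1.0, 10 | 6.3% | 6.1% | 6.8% | 5.2% |
| Skewness 1.5, 8 | 7.8% | 7.6% | 8.9% | 4.7% |
| Skewness 1.5, 10 | 7.4% | 7.2% | 8.5% | 4.3% |
| Exponential, 8 | 10.8% | 10.2% | 12.5% | 5.2% |
| Exponential, 10 | 9.9% | 9.1% | 13.0% | 4.8% |

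The Monte Carlo standard error of an 8% rate is √(0.08 × 0.92 / 10,000) = 0.27 points, so the levels are approximate. The first two columns use the same samples, and at skewness up to 1.5 they differ by 0.2 points at most. For the lognormal shape at n = 10, separate runs gave 7.8% to 8.3% two-stage against 7.8% to 8.4% always-t.

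**5. If the check were run per arm.** With flag rate r in each of three arms, the chance that they do not all get the same test is 1 − r³ − (1 − r)³ = 3r(1 − r). At n = 10:

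- normal, r = 0.051: 3 × 0.051 × 0.949 = 0.145
- gamma shape 4, r = 0.140: 3 × 0.140 × 0.860 = 0.361
- lognormal, r = 0.245: 3 × 0.245 × 0.755 = 0.555

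At n = 8 the last two are 0.295 and 0.458. If the check were pooled over 24 to 30 teeth, the arms could not differ. Shapiro-Wilk would then flag 35% to 45% of samples at skewness 1.0 and 68% to 80% at 1.5.

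**The case against.** The case for leaving the rule alone is substantial, and most of it stands.

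- **No inflation of error.** A reader might infer that choosing the test from the data raises the false positive rate. The figures do not show that. The excess over 5% in the within-arm columns comes from applying a one-sample t-test to skewed changes, and it is there without any switch. The higher rates among samples that pass the check are conditional; the unconditional rate is unchanged. In the two-arm comparison that the trial needs, the two-stage size was 4.3% to 5.2% above, and 4.5% to 5.7% in further runs.
- **Different tests in different arms is not what the protocol says.** The rates of 36% and 56% in step 5 require a per-arm check and separate within-arm tests. Section VII states neither the unit of the check nor whether it uses raw values or changes. A per-arm check is a natural reading of paired tests but not the only one. Once a between-arm test is used, each comparison gets one test and only the summaries could still differ.
- **Which check governs is a detail for the SAP.** At skewness 1.0 to 1.5, Shapiro-Wilk and Kolmogorov-Smirnov disagree in 7% to 14% of samples. A tie-break rule is commonly left to the SAP, which is not at hand, so its absence is not counted here.
- **The choice is not pure chance.** Both branches are written in advance, and most samples would go to the t-test.
- **The primary outcomes are largely untouched.**

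What the objection does not remove is that the step achieves nothing at this sample size. The branch can also matter. With an assumed true change of 0.8 SD, the paired t-test and the signed rank test reached opposite conclusions in about 7% to 11% of samples. Nor does replacing the paired tests with independent-sample versions remove the switch.

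**Conclusion.** The point holds as a minor one. Section VII makes the test and the summary for numerical, mainly secondary, outcomes depend on checks that miss most moderate skewness at 8 to 10 teeth per arm: Shapiro-Wilk flags about 11% to 25% under gamma shape 4 or lognormal sigma 0.5. The two-stage rule has practically the same error rate as always using the t-test, so it gives no protection and does no material harm to that rate. The remaining cost is a possible inconsistency: if normality is checked per arm, one outcome could appear with different tests and summaries across arms.

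These sizes rest on assumed distributions, a 0.05 threshold for the checks, and equal shapes across arms. The more serious issue in the same section is that both branches are paired tests in a three-arm parallel trial. It is a separate point, and removing the switch alone would not cure it.

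**What to change.** In section VII, delete the normality switch and name one between-arm analysis for each numerical outcome: a linear model of the 12-month value on arm and the pre-operative value, reporting the DDM minus blood clot difference with its 95% CI. Show both mean (SD) and median (range) for every arm, whatever the data look like. A permutation or rank-based analysis can be added as an optional sensitivity check.

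The baseline is already collected: the Clinical procedures section schedules a pre-operative periapical radiograph and CBCT, and the follow-up section schedules CBCT at 12 months. With three arms and one covariate the model has four coefficients, leaving 24 − 4 = 20 to 30 − 4 = 26 residual degrees of freedom.

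The cost is about two sentences, no new data and slightly more analysis work. Make the change in the same edit that corrects the paired tests, since the one model serves both purposes.

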double antibiotic paste, ciprofloxacin (Ciprocin 250mg tablets) and Metronidazole (Flagyl 500mg tablets) in a 1:1 ratio will be mixed with sterile distilled water in a 3:1 ratio, then will be introduced into the root canal systems using 18 G hypodermic needle and will be packed gently down the root canal using a hand plunger, ensuring that there will be no remains coronal to CEJ

- A sterile dry cotton pellet will be placed over the paste after which the tooth will be sealed with 3-4mm of a temporary restorative material.
- Patient will be dismissed for 2 week

Second Appointment (two week after 1st visit)

- Response to initial treatment will be assessed. If there are signs/symptoms of persistent infection, additional treatment time with antimicrobial.
- Local Anesthesia without vasoconstrictor will be administered; dental dam isolation will be achieved.
- Copious gentle irrigation will be performed with 20ml of 17% EDTA, followed by a final rinse 20 mL sterile saline.
- Canals will be dried with paper points.

In group I: teeth will be treated with demineralized dentin matrix as scaffold in regenerative endodontic procedure

Teeth, in this group, will be anaesthetised using a local anaesthetic without vasoconstrictor. Demineralized dentin matrix will be introduced inside the root canal and bleeding will be created into root canal by over-instrumentation by rotating K-file at 2 mm past the apical foramen with the goal of having the entire canal filled with blood to the level of the cemento-enamel junction.

A lightly moistened sterile cotton pellet will be placed into the canal, 3-4 mm apical to the CEJ, for 7-10 minutes to allow blood clot formation.

Placement of the bioactive and restorative materials: A bioactive material such as tricalcium silicate will be placed over the blood clot as a capping material. A 3-4 mm layer of glass ionomer will be gently placed over the capping material.

Followed by resin composite restoration ⁽¹⁶⁾.

In group II: teeth will be treated with conventional regenerative endodontic procedure (blood clot scaffold).

Teeth, in this group, will be anaesthetised using a local anaesthetic without vasoconstrictor. Bleeding will be created into root canal by over-instrumentation

A lightly moistened sterile cotton pellet will be placed into the canal, 3-4 mm apical to the CEJ, for 7-10 minutes to allow blood clot formation.

Placement of the bioactive and restorative materials as mentioned above.

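### The stated study dates, October 2023 to October 2024, leave little or no time to enrol 30 teeth before a one-year follow-up

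*Protocol*

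**What the plan says.** The only calendar in the visible protocol is in section VIII, Study timeline: "This study will be conducted from October 2023 to October 2024". It is one span for the whole study, given to the month.

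Other sections fix what must happen inside it:

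- **Follow-up.** The aim is to compare outcomes "in immature permanent incisors with non-vital pulps for one year", and PICOTS also gives one year. Under CBCT evaluation: "CBC with limited field of view will be carried out at 12 month to asses dentin width and length".
- **Number.** Sample size estimation raises the total for "possible dropouts during follow-up intervals to be (30) cases". Grouping has three groups of 10 teeth.
- **Site and enrolment.** Study setting: "This study will be conducted at the Outpatients Clinic at the Department of Pediatric Dentistry and Dental Public Health". Under Screening Recruitment, eligible patients "will be conveniently enrolled in the study until" the target number is met.
- **Visits.** The scaffold goes in at the visit headed "Second Appointment (two week after 1st visit". That section allows further antimicrobial time, of no stated length, if infection persists. The randomisation section has the group revealed only at the final regeneration visit.

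The visible text states no accrual rate, and it does not say from which visit the 12 months are counted.

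**The concern.** A one-year follow-up cannot start for the last tooth until that tooth has been enrolled and treated. A trial that recruits over time therefore needs a calendar longer than its follow-up by at least the recruitment period. Here the calendar is nominally as long as the follow-up alone, and at most one month longer.

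What is at stake is the one-year comparison. If the enrolment and 12-month rules are kept, the study finishes after its stated end. If the end date were kept instead, later teeth would have no 12-month CBCT, and that CBCT supplies a listed secondary outcome (root wall thickness and root length). With 10 teeth per group, each missing assessment is 1/10 = 10% of a group.

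**Working it through.** **Inputs**

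- Calendar: October 2023 to October 2024 (section VIII).
- Follow-up: 12 months (Aim, PICOTS, CBCT evaluation). It takes 366 days here, because 29 February 2024 falls inside.
- First visit to scaffold placement: 14 days, with no extra antimicrobial time (Second Appointment).
- Teeth: 3 groups × 10 = 30 (Grouping), which matches the total under Sample size estimation.

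**Formula**

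Days left for first visits = calendar length − 366 if the year runs from the first visit, or calendar length − 366 − 14 if it runs from placement. Both are shown because the protocol does not fix the origin.

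**Same-date year** (for example 15 October 2023 to 15 October 2024, 366 days)

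- From first visit: 366 − 366 = 0 days.
- From placement: 366 − 366 − 14 = −14 days.

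**Widest reading** (1 October 2023 to 31 October 2024, 396 days elapsed)

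- From first visit: 396 − 366 = 30 days elapsed. First visits run from 1 to 31 October 2023, or 31 days counted inclusively.
- From placement: 396 − 366 − 14 = 16 days elapsed. First visits run from 1 to 17 October 2023, or 17 days counted inclusively.

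**Accrual needed on the widest reading**

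| Origin of the 12 months | Days elapsed (inclusive) | Teeth per week |
|---|---|---|
| Scaffold placement | 16 (17) | 30/16 × 7 = 13.1 (30/17 × 7 = 12.4) |
| First visit | 30 (31) | 30/30 × 7 = 7.0 (30/31 × 7 = 6.8) |

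**Sensitivity**

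- Counting the year as 365 days adds one day to each window: 17 (18) and 31 (32).
- If a tooth needed one extra two-week antimicrobial period (an assumed length) and the year ran from placement, 16 − 14 = 2 days elapsed would remain for its first visit, or 3 counted inclusively.

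**Size of the overrun**

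If first visits are spread over R days from 1 October 2023, the last 12-month assessment falls R − 16 days after 31 October 2024 (year from placement) or R − 30 days after it (year from first visit). Extra antimicrobial time before placement for the last tooth lengthens the placement figure further. For example, at 7 teeth per week R = 30, so the close is 14 days late on the placement origin and on time on the first-visit origin.

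**The case against.** The strongest reply is that the dates are a planning statement, not a rule that governs data. Enrolment runs to the target number, follow-up is one year and the CBCT is at 12 months. Followed as written, the trial ends late with its sample size and comparison unchanged. This stands, and it is why the severity is low.

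A second reply is that the widest reading does hold a full year plus 16 to 30 days, so the plan is not arithmetically impossible. This also stands. The pace can be called unrealistic only as a judgement, because no accrual rate or clinic volume is given to test it. A child may also contribute more than one tooth: the inclusion criteria admit children with one or more eligible teeth, and allocation is by tooth. The number of children needed per week could then be lower, although Clinical procedures speaks of a single selected tooth per child.

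Third, a figure near the end of the protocol is not shown and might hold a schedule. It could contain the missing breakdown, so the lack of one in the visible text is not held against the plan. The written dates would still need to agree with it.

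A reader might also infer three stronger things that the document does not support:

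- **That follow-up will be cut at October 2024, or that this would favour one group.** No text imposes such a cut. Because allocation is in randomised blocks, a cut would cost information and the one-year comparison rather than clearly favour a group.
- **That the calendar falls short of the follow-up year itself.** This needs the latest possible start in October 2023 paired with the earliest possible end in October 2024. The month-level wording gives no reason to pair them so.
- **That the dates cover recruitment only, so there is no problem.** The sentence describes the conduct of the study, under a heading for its timeline, and nothing limits it to recruitment.

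**Conclusion.** The stated dates and the one-year follow-up need to be reconciled. On a same-date year there is no recruitment time: 0 days from the first visit, and 14 days short from placement. On the widest reading all 30 first visits must fall within 16–17 days (year from placement) or 30–31 days (year from first visit), before any extra antimicrobial time.

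These figures assume visits exactly 14 days apart and a 12-month assessment held on its due date. That the widest reading is infeasible in practice is a judgement. It rests on narrow eligibility, one clinic and one examining operator, against a need of about 12–13 or 7 teeth per week.

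The likely consequence is an overrun of the stated dates. Only if the end date were enforced would later teeth lose the 12-month assessment. Severity is low.

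**What to change.** Replace the single date range in section VIII with a recruitment period followed by the follow-up period. State from which visit the 12 months are counted, for example the visit at which the group is revealed. Define study end as the 12-month assessment of the last enrolled tooth. If the figure not shown already holds such a schedule, bring the written dates into line with it.

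The cost is a later close and a protocol amendment. The route exists under Protocol amendments, where the ethics committee and review board "will review and approve the changes of protocol before proceeding and implementation of changes". On the widest reading the delay is the length of recruitment in days minus 16 or minus 30, depending on the origin chosen, plus any extra antimicrobial time that puts back placement. No extra patients or procedures are needed.
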